### 1. Background:

Operations on cutaneous tissues of the head and neck are some of the most frequently 27 performed types of operation performed. They can often successfully be performed using 28 29 local anaesthetic (LA). However, tissues in this anatomic area are some of most sensitive tissues in the body to nociceptive pain. As such, local anaesthetic can be a distressing 30 experience for patients in many ways. Unfortunately, it is also the most common anatomical 31 site for cutaneous malignancies. Advanced age and chronic sun exposure are two potent risk 32 factors. The majority of these lesions are resected under local anaesthetic for several reasons 33 34 including economic, patient-factors, theatre availability and speed. However, one of the major disadvantages of local anaesthetic such as lidocaine is pain during administration. This 35 is exacerbated as the head and neck area is one of the most sensitive parts of the body. 36 37 Several interventions have been used to reduce pain from needles and injections including ethylene chloride cryoanalgesic spray and topical anaesthetic agents including EMLA 38 39 (lidocaine and prilocaine) and Ametop ointments. These have been extensively used in paediatric populations with great success to reduce pain during procedures requiring 40 hypodermics such as cannulation. Several studies have trialled these interventions in adult 41 42 populations across a variety of anatomical locations with variable results.

43

44 1.1.**Hypothesis**:

45

46

#### 47 **1.2.** Aim

The aim of this study is to assess if ethylene chloride or EMLA are effective in reducing thepain associated with local anaesthetic administration

EMLA and ethyl chloride reduce pain associated with local anaesthetic administration

50

# 2. Outcome Measures

52	2.1. Primary outcome measure:
53	The primary outcome measure is patient reported pain on a numeric rating scale (NRS) (1; no
54	pain, 10; worst pain imaginable)
55	
56	2.2. Secondary outcome measures:
57	Patient satisfaction measured on NRS scale of 1=not bad at all, to 10=worst experience
58	imaginable.
59	Analysis of risk factors associated with pain from local anaesthetic in the head and neck
60	including size of resection and injection volume:
61	• Pathology – malignant versus benign
62	Local anaesthetic volume
63	• Size of resection
64	• Site of resection
65	
66	
67	3. Methodological design
68	3.1. Study design
69	Randomized controlled trial
70	
71	3.2. Selection:
72	Patients will be selected from those attending scheduled excision of cutaneous head and neck
73	malignancies at our centre
74	
75	3.3. Inclusion criteria:

76	• Aged at least 18 years
77	• Receiving surgery to cutaneous tissues of the head and neck
78	Procedure performed under local anaesthetic
79	
80	3.4. Exclusion criteria:
81	Paediatric patients
82	• Surgery performed under general anaesthetic
83	• Mucosal operative site (e.g. oral cavity)
84	• Significant cognitive impairment (e.g. severe dementia)
85	Known sensitivity/allergy to EMLA
86	• History of a pain disorder (e.g. complex regional pain syndrome).
87	
88	3.5. Sample size calculation:
89	A formal sample size calculation will be performed after an initial pilot study of ten patients
90	per group to calculate the effect size. Other studies on using topical anaesthetic agents in
91	other non head and neck anatomical sites typically required less than 50 participants per
92	group. G*Power 3.1 (Universität Düsseldorf) software will be used to calculate the necessary
93	sample size. We will likely employ an $\alpha$ error probability of 0.05 and a power of 95%. A 10%
94	margin for safety will be used to mitigate the possible risks of participant attrition
95	
96	3.6. Randomization:
97	Computer randomization will be performed. A random number sequence will be generated
98	using randomizer.org® with numbers allocated using stratified permuted blocks of four and
99	these will be concealed in individual sealed envelopes with the aid of a research contributor.

100	Participants will be allocated in order of recruitment and in participants with more than two
101	lesions will have the more superiorly located lesion allocated first.
102	
103	3.7. Interventions
104	Patients will be split into 4 groups:
105	• EMLA
106	Aqueous ointment
107	• Ethyl chloride spray
108	• no treatment.
109	
110	3.8. Study procedures
111	Written informed consent will be obtained prior to group allocation. Following group
112	allocation, topical agents will be administered as follows. EMLA (EMLA cream 5% 25g
113	lidocaine, 25g prilocaine) and aqueous cream will be applied to cover the surgical site,
114	delivered via an unmarked syringe to achieve single blinding. A Tegaderm® adhesive
115	dressing will then be applied over this to prevent the cream from drying out, and it will be
116	removed in the theatre before the administration of LA. The local anesthetic to be used will
117	be 1% lidocaine with 1:200,000 adrenaline and will be injected via a 25-gauge needle
118	attached to a 10ml syringe. A 5ml syringe will be occasionally used when it is not possible to
119	inject via a 10ml syringe.
120	EC will be applied to the surgical site before LA injection. The area will be sprayed at a
121	distance of 5-10cm for 4-8 seconds until the skin slightly blanches, and the fluid will be
122	allowed to evaporate.

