## 133 4. Statistical analysis

The distribution pattern of variables will be assessed using the Kolmogorov-Smirnov test. 134 The Kruskal-Wallis test and Mann Whitney test will be employed to compare groups for non-135 parametric data and for covariate analysis. The Chi-squared test will be applied to detect 136 differences for categorical data. Spearman's Rho will be used to quantify the strength of the 137 138 linear relationship between non-parametric continuous variables. A per protocol analysis will be conducted as it is believed that in cases where patients are unable to describe their pain by 139 using a number, it will disproportionately affect the results by conducting a "worst case 140 141 scenario" analysis. Furthermore, due to a minimal interval between intervention and measurement of pain outcomes in this study, there will be low rates of attrition. Statistical 142 analysis will be performed using SPSS v.26 (Aramonk, US). Statistical significance will be 143 144 considered at p < 0.05.

145

- 146
- 147
- 148

149

150	5. Miscellaneous
151	5.1. Ethical considerations:
152	This trial will be registered with the University Hospital Waterford Research and Ethics
153	Committee where full ethical approval will be obtained prior to study commencement. It
154	is considered that patient risks from this study are negligible.
155	
156	5.2. Funding:
157	No funding will be necessary for this study
158	
159	5.3. Dissemination of results
160	Results will be prepared into a scientific manuscript for publication and presented at

161 scientific surgical meetings

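### Whether the allocated method can be applied at a lesion emerges only after allocation, so a per-protocol analysis could lose lesions unevenly by arm and by site

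*Combined protocol and SAP*

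**What the plan says.** **Eligibility.** Section 3.3 takes patients "Receiving surgery to cutaneous tissues of the head and neck", with no limit by sub-site. In section 3.4 the only anatomical exclusion is "Mucosal operative site (e.g. oral cavity"), and the only exclusion tied to a study agent is "Known sensitivity/allergy to EMLA". Neither section asks whether a cream, a dressing or a spray can be applied at the lesion.

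**Order and method of application.** Section 3.8 puts treatment after "allocation, topical agents will be administered as follows". For EMLA and aqueous cream, the site is covered with cream and an adhesive "dressing will then be applied over this to prevent the cream from drying out, and it will be" taken off in theatre. For ethyl chloride, the spray is given from a "distance of 5-10cm for 4-8 seconds until the skin slightly blanches, and the fluid will be" left to evaporate. The fourth arm in section 3.7 receives nothing. Section 3.8 allows a smaller syringe where access for the injection is difficult, but has no equivalent provision for the topical agents.

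**Analysis.** Section 4 states that "A per protocol analysis will" be carried out. The reason given concerns patients who cannot put a number on their pain. Low attrition is argued from the short time between intervention and pain score. No section says how an allocation that was not delivered is recorded, replaced or analysed.

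**Site and pain.** Section 2.2 lists site of resection among the possible risk factors for injection pain. Section 3.6 mentions stratification but does not name the factor.

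**The concern.** The arms place different demands on the lesion site, and whether those demands can be met becomes apparent only once the arm is known. If a method turns out not to be usable, the loss falls on a treated arm. It cannot fall on the no-treatment arm, where there is nothing to deliver. Any such losses would also cluster at the sites where the method is difficult.

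In its ordinary meaning, a per-protocol analysis removes those lesions from the treated arm and keeps the comparable lesions in the untreated arm. The groups would then differ in site mix, and the plan itself treats site as a candidate predictor of the outcome. The planned Kruskal-Wallis and Mann-Whitney group comparisons do not adjust for site. Stratifying the randomisation, even by site, would not restore balance once lesions are dropped after allocation.

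At stake is the fairness of the comparisons with no treatment and of every comparison involving ethyl chloride, which is one of the two agents named in the aim (section 1.2).

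**Working it through.** The plan states no site distribution, non-delivery rate, standard deviation or final sample size, so it has no figure of its own to reproduce. The arithmetic below shows the possible size on assumed inputs.

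**Step 1. Which comparisons are exposed** (from sections 3.7 and 3.8)

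| Comparison | Delivery demands | Could loss differ between arms? |
|---|---|---|
| EMLA vs aqueous cream | the same in both arms | largely not; the same sites would be affected |
| EMLA or aqueous cream vs no treatment | cream and dressing vs nothing | yes, loss in the cream arm only |
| Ethyl chloride vs no treatment | spray vs nothing | yes, loss in the spray arm only |
| Ethyl chloride vs either cream | spray vs cream and dressing | yes, if the difficult sites are not the same |

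**Step 2. Bias in the mean pain score, treated vs untreated, with no true effect**

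Assumed inputs:
- p: share of lesions at sites where the arm's method cannot be applied
- l: share of those lesions dropped from the treated arm
- D: how many NRS points higher those sites score

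Let m be the mean at the other sites.
- Untreated arm mean: m + pD
- Retained treated arm mean: m + p(1 − l)D / (1 − pl)
- Bias = pD − p(1 − l)D / (1 − pl), which is pD when l = 100%

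| p | l | D | Bias (points) |
|---|---|---|---|
| 5% | 100% | 1 | 0.05 × 1 = 0.05 |
| 10% | 100% | 2 | 0.10 × 2 = 0.20 |
| 20% | 50% | 2 | 0.40 − 0.20/0.90 = 0.18 |
| 20% | 100% | 2 | 0.20 × 2 = 0.40 |

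A positive D flatters the treated arm. A negative D works against it.

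**Step 3. False-positive rate**

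Further assumptions: SD 2.5, 50 lesions per group (section 3.5 says that comparable studies needed fewer than 50), two-sided 5% test of means.
- p = 10%, D = 2, all lost: 45 remain. SE = 2.5 × √(1/50 + 1/45) = 0.514. Shift = 0.20/0.514 = 0.39 SE. The rejection rate is about 7%.
- p = 20%, D = 2, all lost: 40 remain. SE = 2.5 × √(1/50 + 1/40) = 0.530. Shift = 0.40/0.530 = 0.75 SE. The rejection rate is about 12%.
- p = 5%, D = 1, all lost: the rate stays at about 5%.

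**Step 4. Power**

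At 95% power (section 3.5), 50 per group corresponds to a standardised difference of (1.960 + 1.645) × √(2/50) = 0.72. With the 10% margin, 50/0.9 gives 56 allocated per group. Losing 20% of one arm leaves power at about 95%. Losing 20% of both compared arms leaves about 93%. The issue is therefore bias, not lost power.

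**The case against.** The strongest objection is that the documents nowhere say that any of the methods fails at any head and neck site. They list no difficult sites and give no rate. A reader might infer that lesions will be lost; the text supports only that they could be. Some sites next to mucosa may already be out, because the oral cavity is given as an example of the mucosal exclusion and not as its limit. Both points stand.

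Second, the bias does not come from eligibility alone. It needs the per-protocol set to drop undelivered allocations, and section 4 does not define that set; its stated reason is a different one. If every lesion is analysed as allocated, this bias disappears with no change to section 3.4. That also stands, and it is why the analysis change comes first in the fix. But per protocol ordinarily means excluding those who did not receive the allocated treatment, and the plan offers no other analysis.

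Third, a reader might infer that EMLA would look better than it is in every comparison. The documents do not support that: EMLA and aqueous cream are delivered in the same way, so that blinded comparison is largely unaffected.

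Fourth, the size rests entirely on assumed inputs, and the calculation is on means while section 4 plans rank tests for non-parametric data. The figures are therefore indicative. Removing higher-scoring lesions from one arm would shift a rank comparison in the same direction, but not by an amount that these figures give.

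**Conclusion.** The gap is real but conditional. Broad site eligibility, arm-specific delivery after allocation, the absence of any rule for non-delivery and a sole per-protocol analysis are all in the text. Together they allow losses that differ by arm and by site. That such losses will occur is not in the text.

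On the assumed inputs, the bias against no treatment runs from 0.05 points, which is negligible, to 0.4 points on the 1–10 scale. The top of that range needs one lesion in five to be at a difficult site, all of them to be dropped, and those sites to score 2 points higher. The direction favours the treated arm only if the lost sites hurt more. Ethyl chloride against cream is also exposed if the difficult sites differ between methods. The change is worth making because it is cheap, and because a judgement of deliverability made after the envelope is opened is no longer blind to the arm.

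**What to change.** 1. **Section 4.** Make the primary analysis all randomised lesions with a recorded pain score, each in its allocated arm, whether or not the agent was delivered. Collect the pain score after injection in every one of them. Keep per protocol as a sensitivity analysis and define its population. Patients who cannot give a number can still be handled without a worst-case substitution, so the reason stated in section 4 does not stand in the way.
2. **Sections 3.4 and 3.6.** Before the envelope is opened, have the operator record whether all four allocations in section 3.7 could be delivered at this lesion as section 3.8 describes. Enrol only lesions for which the answer is yes.
3. **Reporting.** Log lesions excluded at this check by site, and any later non-delivery by arm and site.

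Which sites are suitable is left to the investigators.

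The cost is one eligibility line, a tick box and a revised sentence in section 4. A few lesions will not be enrolled, and the conclusion will cover sites where all four options are feasible. Keeping undelivered allocations in their arm dilutes a true effect roughly in proportion to the share undelivered; the check before allocation should keep that share small.

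### The sensitivity exclusion in section 3.4 covers EMLA only, although an eligible patient can also be randomised to ethyl chloride, the other active agent

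*Combined protocol and SAP*

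**What the plan says.** Section 3.4 lists six exclusions: children, general anaesthesia, a mucosal site, significant cognitive impairment, a history of a pain disorder, and "Known sensitivity/allergy to EMLA". The last is the only one that concerns tolerance of a study material.

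The hypothesis in section 1 gives the two active agents equal standing: "EMLA and ethyl chloride reduce pain associated with local anaesthetic administration". Section 3.7 states "Patients will be split into 4 groups". Besides EMLA and no treatment, these include "Ethyl chloride spray" and "Aqueous ointment".

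Section 3.8 describes the exposure. For the spray, "EC will be applied to the surgical site before LA injection", and spraying continues until the skin blanches slightly. EMLA and the aqueous product are both spread over the site and then covered: "A Tegaderm® adhesive" dressing goes on top. Section 3.8 also places written consent before group allocation.

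**The concern.** A patient should enter a randomised comparison only if every possible allocation is acceptable for that patient. By excluding known EMLA sensitivity, the protocol adopts this principle for one active agent. It does not extend it to the other, although both are put on the skin at the operative site and both carry the trial's hypothesis.

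Two things are at stake. One is avoidable exposure of a patient with a known problem. The other is a departure from allocation that could have been settled beforehand. If the question comes up only after the envelope is opened, the patient is already randomised. Section 4 plans a per protocol analysis, so a patient who does not receive the allocated treatment could be left out of it. Asked at consent, the same question gives a plain exclusion before randomisation.

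**Working it through.** The plan states no figure on this point, so there is nothing to reproduce. The check sets the exclusion list in 3.4 beside the materials used under 3.7 and 3.8.

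| Material | Where it is used | Sensitivity criterion in 3.4 |
|---|---|---|
| EMLA | EMLA group | Yes |
| Ethyl chloride | Spray group | None |
| Aqueous cream | Aqueous group | None |
| Adhesive dressing | EMLA and aqueous groups | None |

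Two readings are built into the table. The aqueous product is called an ointment in 3.7 and a cream in 3.8, and I take these to be the same product. The dressing sentence directly follows the one naming both creams and refers back to it, so I take it to cover both cream groups. A narrower reading, with the dressing used over EMLA only, would leave the dressing unscreened in one group instead of two. It would not change the ethyl chloride point.

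Now follow a patient with a known sensitivity or contraindication to ethyl chloride who meets the inclusion criteria.

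1. None of the six items in 3.4 removes this patient on that ground.
2. Consent is taken (3.8). The visible text describes no further tolerance check at this step.
3. The envelope is opened (3.6). If each permuted block of four holds one place per group, as the block size suggests but the text does not state, the chance of drawing the spray is 1/4 = 25%. This is the chance for a patient who already has the problem. It says nothing about how many such patients there are.
4. If the spray is drawn, either it is applied or staff depart from the allocation. The protocol describes neither course. They are the two possibilities left open once the patient has been randomised.

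The table is a cross-check of coverage and not a measure of risk, because a drug product, a spray, an emollient and a dressing do not carry equal weight. The number of patients affected would need the frequency of these sensitivities in the recruited population, which the documents do not give.

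**The case against.** The strongest case on the other side is that only a difference in wording has been shown. The documents say nothing about reactions to ethyl chloride, aqueous cream or the dressing. EMLA contains two local anaesthetics and may merit a named exclusion that an emollient does not. Section 5.1 judges patient risk to be negligible and makes the study subject to full ethical approval. Staff may use clinical judgement, and a patient can declare a sensitivity at consent. Consent pages are not among the material available for review, and allergy questions could appear there.

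Much of this stands. It limits the size of the point and makes the aqueous cream and dressing secondary. It also means that the absence of a check can be asserted only for the visible text. It does not remove the gap for ethyl chloride. The statement in 5.1 is a general judgement and not a screen, and it does not explain why one active agent has a sensitivity criterion and the other has none. Clinical judgement used after allocation does not do the work of an eligibility rule applied before it.

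Two stronger readings are tempting, and the documents do not support them.

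- A reader might infer that blinding prevents patients from protecting themselves, because the creams are "delivered via an unmarked syringe to achieve single blinding". A known sensitivity can still be declared at consent, before allocation. No blinding of the spray is described, and the dressing is not hidden by the syringe.
- A reader might infer that the resulting losses would bias the per protocol comparison or use up the 10% attrition margin in 3.5. No frequency is given, and the sample size is deferred until after the pilot, so the losses cannot be set against that margin in either direction. Section 4 justifies the per protocol analysis by patients who cannot put a number on their pain, and it expects little attrition.

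**Conclusion.** The point holds as a minor patient-safety and eligibility improvement. Followed literally, 3.4 admits a patient with a known sensitivity or contraindication to ethyl chloride to a randomisation that can allocate that agent. The aqueous cream and the dressing share the gap with less force.

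No effect on power, type I error or bias is claimed, and no number of affected patients is estimated. Nothing in the documents suggests that staff would knowingly apply a material to a patient with a known reaction. The conclusion assumes that the exclusion list in 3.4 is complete as shown and that no separate check is laid down in the consent material. If one is, the remaining task is only to bring 3.4 into line with it.

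**What to change.** Replace the EMLA item in 3.4 with: known sensitivity or contraindication to any study agent (EMLA, ethyl chloride, aqueous cream) or to the adhesive dressing. State in 3.8 that this is checked at consent, before the envelope is opened. What counts as a contraindication is for the investigators to specify.

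The cost is one line in the exclusion list and one screening question. A few patients may become ineligible. The documents do not allow that number to be estimated, but each would be a patient for whom at least one allocation was unsuitable. The arms, the outcome measures, the significance level and the power target stay as they are.

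### Section 3.5 sets n from the effect seen in a pilot of ten per group, with no target NRS difference; if that raw estimate is used and the pilot kept separate, average power falls short of 95%

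*Combined protocol and SAP*

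**What the plan says.** Section 3.5 is the whole of the sample size plan. "A formal sample size calculation will be performed after an initial pilot study of ten patients" "per group to calculate the effect size", after which G*Power will give n. The settings are described as likely rather than fixed: an "error probability of 0.05 and a power of 95"%. A 10% "margin for safety will be used to mitigate the possible risks of participant attrition".

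The endpoint is in section 2.1: "The primary outcome measure is patient reported pain on a numeric rating scale (NRS"), scored 1 to 10. Section 3.7 lists four groups. Section 4 names the tests: "The Kruskal-Wallis test and Mann Whitney test will be employed to compare groups", with significance "considered at p < 0.05".

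The document gives no NRS difference worth detecting, no SD, no n, no sidedness, no test or comparison for the sizing, and no minimum or maximum n. It remarks that studies at other anatomical sites usually needed fewer than 50 per group, but sets neither a target nor a cap from this. It does not say whether the pilot patients are part of the final analysis.

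**The concern.** The stated purpose of the pilot is to supply the effect size, and no other input is named. The plain reading is that the observed pilot effect is entered into G*Power as if it were the truth. Ten per group is too few for that. When the pilot overestimates the effect, the main trial is too small; when it underestimates, the trial is too large. The two errors do not cancel, because power cannot exceed 100%.

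What is at stake is how a null result can be read. With no target difference, nobody can say which effect the trial was built to detect, and an optimistic pilot can leave the trial too small without anyone noticing. A pessimistic pilot can call for hundreds per group at one centre. If pilot patients are also analysed, the data that set n are used again in the test, which affects the type I error.

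**Working it through.** The plan gives no n, so there is no figure to reproduce. The check asks what power results when section 3.5 is followed on its plain reading.

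**Inputs from the plan:** pilot of 10 per group; alpha 0.05; power 95%; margin 10%; four groups; Mann-Whitney and Kruskal-Wallis tests.

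**Assumed:** two-sided test; equal allocation; normal data; true differences of 0.5 to 1.5 SD; efficiency of 0.955 for Mann-Whitney relative to the t test.

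**Needed n per group.** n = 2(1.960 + 1.645)² / (0.955 d²) = 27.21/d². This gives 109, 43, 28, 19 and 13 at d = 0.5, 0.8, 1.0, 1.2 and 1.5.

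**Why the errors do not cancel.** Power at true d is Φ(d√(0.955n/2) − 1.960). Take a true d of 0.8 and two pilots that miss by 0.4 in opposite directions:
- Pilot d = 1.2: n = 27.21/1.44, so 19. Power = Φ(2.41 − 1.96) = 0.67.
- Pilot d = 0.4: n = 27.21/0.16, so 171. Power is about 1.00.

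Their average is 0.84, not 0.95. Power drops below 80% once n is 25 or less (0.79 at 25, 0.80 at 26), that is, once the pilot estimate exceeds about 1.04 SD.

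**Separate pilot, two groups** (200,000 simulated pilots per effect, absolute observed d entered, no cap):

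| True d | Mean power, no margin, no floor | Mean power, 10% margin, floor of 10, no dropout |
|---|---|---|
| 0.5 | 0.79 | 0.81 |
| 0.8 | 0.84 | 0.87 |
| 1.0 | 0.86 | 0.90 |
| 1.2 | 0.88 | 0.92 |
| 1.5 | 0.90 | 0.96 |

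The margin is applied as n/0.9. At 0.8 SD:
- 95% of pilot estimates lie between about −0.07 and 1.89 SD.
- The median n is 42 against 43 needed, so n is centred correctly. Its 10th and 90th percentiles are 13 and about 425.
- Without the margin, 49% of pilots give at least 95% power and 32% give under 80%. With the margin, 27% give under 80%.

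**Sensitivity.**
- A cap of 50 per group, without the margin, lowers mean power to 0.61 at 0.5 SD and 0.83 at 0.8 SD.
- On a rounded 1 to 10 scale with ties (assumed SD 2.5, control centre 5), mean power is 0.78, 0.83 and 0.84 at 0.49, 0.79 and 1.02 SD.
- If a four-group f is entered instead, the pilot f is biased upward (median 0.34 when the truth is 0.25). Mean power is 0.70 at f = 0.25 (median n 38 against 70 needed) and 0.82 at f = 0.40 (22 against 28).

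**Pilot patients pooled into the final analysis** (two-group t test, pilot counted within n, uncapped): power is about 0.90 to 0.91 at 0.5 SD, about 0.95 at 0.65 SD and 0.97 to 0.98 at 0.8 SD. With no true difference the rejection rate is about 7% instead of 5%. If n further patients are added to the pilot, it is about 6%. For a four-group analysis of variance with the margin, the shortfall ends at about 0.7 to 0.8 SD and the type I error is about 7%.

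**The case against.** A reader might infer that the plan simply fails to deliver 95% power for every true difference up to about 1.2 SD. The documents do not support that as an unconditional statement, for two reasons. That range requires the pilot to be separate from the final analysis, which section 3.5 leaves open; if pilot patients are pooled, the shortfall ends much earlier and the defect becomes one of type I error. It also requires the raw estimate to go in unadjusted. That is the natural reading, but the calculation is still to come and its test and comparison are not named.

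Three further points deserve weight. The plan commits to a 10% margin and section 4 expects little attrition, so the figures without a margin are the harsher end; the margin narrows the gap without closing it over 0.5 to 1.2 SD. With a floor of ten per group, which the plan does not state, effects of 1.5 SD or more reach about 95% anyway. And 95% is a high and tentative target: averages of 0.81 to 0.92 would satisfy a common 80% standard. That last point does not dispose of the matter, because an average conceals the 27% to 32% of pilots at 0.8 SD that lead to less than 80% power.

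**Conclusion.** The concern holds in conditional form, and section 3.5 should be changed. No target NRS difference is stated and the role of the pilot patients is undefined; both follow directly from the text. With a separate pilot and the raw estimate, average two-group power is about 0.79 to 0.88 over 0.5 to 1.2 SD, or 0.81 to 0.92 on the more favourable settings, against a likely 95%. With pooling and no cap on n, power recovers from about 0.65 to 0.8 SD upward, at the price of a 6% to 7% type I error. Each reading leaves a defect.

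It would be wrong to conclude that n is systematically too small in the two-group case: it is centred correctly, and about half of pilots give at least 95% power. The problem is its spread.

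Confidence is medium. The use of the raw estimate, the true effects, the two-sided test and the sizing test are assumptions, and effects are in SD units because the documents give no NRS SD.

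**What to change.** Rewrite section 3.5, keeping the same pilot and software:
1. Before the pilot, state the NRS difference worth detecting and the comparison it applies to.
2. Use the pilot only to estimate the SD, pooled within the four groups (4 × 9 = 36 degrees of freedom if all four are piloted).
3. Compute n from those two numbers for the planned test, and describe the 95% power as conditional on them.
4. State whether pilot patients enter the final analysis, and exclude them if pilot arm means are used to set n.

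**Gain.** When the target equals the truth at 0.8 SD, the 10th to 90th percentile range of n is 31 to 56, mean power is 0.935, and about 2% of pilots lead to under 80% power instead of 32%.

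**Cost.** The sponsor must commit to a target in advance, and power is protected only for effects at least that large: n = 43, set for 0.8 SD, gives Φ(0.5√(0.955 × 43/2) − 1.960) = 0.62 if the truth is 0.5 SD. Even at the target, power averages about 93% to 94% before the margin because the SD is estimated; keeping the 10% margin with no dropout brings it to about 95%. The target also drives the size: for 1.5 NRS points and an assumed SD of 2 to 3 (d = 0.75 to 0.5), n = 27.21/d² is 49 to 109 per group before the margin.
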